#### 2. SYNOPSIS

Name of Sponsor:			
The Surgeon General, Department of the Army			
Name of Investigational Product: RePlas TM			
Name of Active Ingredient: Human Plasma, Freeze Dried			
Title of Study: A Phase 1, Single-Center, Partial Double-Blind, Randomized, Controlled (versus Fresh Frozen Plasma [FFP] in Cohort 3 only) Clinical Study of the Safety of Ascending Doses of Autologous Freeze Dried Plasma (FDP) in Healthy Volunteers			
Study Center(s): Hoxworth Blood Center/University of Cincinnati			
Principal Investigator: [name], PhD			
Study Period (years): Estimated date first subject enrolled: February 2017 Estimated date last subject completed: July 2018	Phase of Development: 1		

#### **Objectives:**

**Primary:** The primary objective of this study is to assess the safety of single infusions with the RePlasTM FDP product at increasing fixed doses of either 1 unit (approximately 270 mL), 2 units (approximately 540 mL), or 3 units (approximately 810 mL) in normal healthy subjects. In the 2 lower dose cohorts, safety will also be assessed in terms of the type of autologous plasma used as the starting material in the manufacture of the investigational product:

- RePlasTM FDP product manufactured from autologous FFP derived from whole blood (WB) donations where Citrate Phosphate Dextrose (CPD) is the anticoagulant, or RePlasTM FDP-CPD; and
- RePlasTM FDP product manufactured from autologous FFP collected during plasmapheresis where Acid Citrate Dextrose (ACD) is the anticoagulant, or RePlasTM FDP-ACD.

The highest dose cohort will receive FDP manufactured only from FFP collected by plasmapheresis (FDP-ACD). Conclusions on whether the study meets its safety objectives will be based only on treatment emergent adverse events (TEAEs). TEAEs are adverse events (AEs) that occur after administration of the study treatment, plasma infusion, has begun. AEs occurring prior to treatment (e.g., AEs that occur during autologous plasma collection) will not be considered relevant to the study's objectives.

Secondary: The secondary objectives are to:

Assess the safety of a fixed-dose infusion of 3 FDP units (approximately 810 mL) in
comparison to infusion with the same dose of autologous FFP collected during
plasmapheresis; and

Determine if the changes in specific coagulation factors, hematology, and chemistry values
are similar within clinically meaningful levels after infusion of either 3 units of autologous
FDP or FFP.

#### Methodology:

**Overview.** This single-site, partial double-blind study in healthy volunteers is designed to assess the safety of infusing ascending doses of reconstituted autologous FDP in 3 fixed-dose cohorts. Subjects in Cohort 1 will receive 1 unit of FDP, which is approximately 270 mL. Subjects in Cohort 2 will receive 2 units of FDP, which is approximately 540 mL. Subjects will be enrolled for a specific dose cohort beginning with the lowest dose in Cohort 1. In the absence of TEAEs or implementation of protocol stopping rules (SR), subjects will be enrolled in Cohort 2. In both Cohorts 1 and 2, subjects will be methodically assigned to 1 of 2 single infusion treatment arms where they will receive the corresponding dose of either FDP-CPD or FDP-ACD, products manufactured with autologous plasma derived from WB or autologous plasma collected by plasmapheresis.

In the absence of TEAEs or implementation of protocol stopping rules (SR) in Cohort 2 subjects, infusions in Cohort 3 subjects may proceed. These subjects will receive 3 autologous FDP-ACD units (approximately 810 mL), which is the highest trial dose of the experimental product and undergo an additional separate infusion where they will receive the same dose of autologous FFP. Subjects participating in this randomized, controlled, crossover infusion treatment cohort will be randomized to a specific infusion schedule where they will first be infused with either 3 units of FDP or 3 units of FFP at the first infusion visit, followed by infusion with the alternate product at the second infusion visit. Crossover treatment of FDP and FFP enables comparison of infusion safety parameters and select coagulation factor recoveries between FDP and FFP within the same subject at this higher dose. Unlike Cohorts 1 and 2, the FDP and FFP infusion products in Cohort 3 will be sourced only from autologous plasmapheresis donations. A 2-week period between infusion visits is required for all Cohort 3 subjects regardless of the infusion schedule.

Collection of Autologous Plasma. Use of autologous plasma in the trial assists in the elimination of potential AEs related to allogeneic plasma infusion, but it also adds additional burden to participating subjects who, upon consent and enrollment, need to donate sufficient volume of plasma to provide the autologous plasma needed for the trial infusions (eg, manufacture of autologous FDP units in all cohorts; in Cohort 3, the additional need for FFP in addition to FDP). Blood donation standards typically require a 56-day interval between WB donations; however, an abbreviated donation period of 28 days will be in use for the duration of this study. Without the loss of red blood cells (RBCs) in plasmapheresis, these types of donations can be made more frequently, with an approximate 7 to 10 day interval between donations. Also, depending on the donor's size, plasmapheresis donations yield greater plasma volume per collection. Summarily, compared to WB collection, the use of plasmapheresis to net the per subject plasma volume required presents practical advantages to subjects (eg, requires fewer collection visits) while minimizing increased risk for Cohort 3 subjects. FDA's volume limits for automated collection of plasma are summarized and presented in the Collection Volume Limits via Plasmapheresis Collection table below (FDA-1992).

#### Collection Volume Limits via Plasmapheresis Collection

Donor Weight	Plasma Volume or Weight	Collection Volume*
10 – 149 lbs	625 mL (640 g)	690 mL (705 g)
150-174 lbs	750 mL (770 g)	825 mL (845 g)
≥175 lbs	800 mL (820 g)	880 mL (900 g)

\*includes anticoagulant volume

As shown in the Cohort and Treatment Arm Details table below, subjects' assigned cohorts and treatment arms indicate the type, frequency, and total volume of blood/plasma donations required. Subjects in Cohorts 1 and 2 are to provide sufficient plasma volume for a single infusion with either 1 or 2 units, respectively, and based on assigned treatment arm, they are to provide plasma through WB

or plasmapheresis collection for manufacture of autologous FDP-CPD or FDP-ACD. Cohort 2 subjects in the FDP-CPD treatment arm are required to successfully make 2 WB donations within a relatively short period of time to provide adequate volume for their use in the trial. Because of the extraordinarily long time required to accrue sufficient WB-derived plasma for the high dose cohort (approximately 11 months), the FDP-CPD treatment arm is not included in Cohort 3. The total starting volume of plasma needed from each Cohort 3 subject is approximately 1,620 mL; triple that of Cohort 2 and thus inclusion of this treatment arm in Cohort 3 would require 6 WB donations, increasing subject risk for significant iron store depletion and anemia.

#### **Cohort and Treatment Arm Details**

Dose Cohorts and Treatment Arms	Number of Subjects	Donation Type	Approximate Volume Autologous Plasma Required	Number of Donations
Cohort 1: One unit single infusion	on [approxima	tely 270 mL]		
Arm 1: FDP-CPD	4	WB	270	1
Arm 2: FDP-ACD	4	Plasmapheresis	270	1
Cohort 2: Two units single infusion [approximately 540 mL]				
Arm 3: FDP-CPD	4	WB	540	2
Arm 4: FDP-ACD	4	Plasmapheresis	540	1
Cohort 3: Three units crossover infusion [approximately 810 mL, each]				
Arm 5: FDP-ACD x FFP	4	Plasmapheresis	1,620	3-41
Arm 6: FFP x FDP-ACD	4	Plasmapheresis	1,620	3-41

<sup>1 Assumes an average range of 600 to 800 mL donation volume.

#### Pharmacovigilance.

The study will be paused to assess the safety of study continuation using the following SRs that will be applied to all study subjects throughout the trial:

- 1. An SAE that is determined to be possibly, probably, or definitely related to the study product;
- 2. An AE related to the study product that the PI, RM, and/or the sponsor's PVG MD agree jeopardizes the subject's health or safety;
- 3. An AE related to the study product that requires medical or surgical intervention to prevent occurrence of an SAE;
  - 4. A post-infusion, coagulation function assay result that is abnormal and also greater than a 20% change from the baseline value recorded for prothrombin time and international normalized ratio (PT/INR) and/or activated partial thromboplastin time (aPTT) (eg, a subject who has a baseline INR of 1.0 with a post-infusion INR of 1.3 will activate an SR, because this is an abnormal coagulation function assay result that is also a greater than 20% change from the pre-infusion assay result); and/or
- 5. Post-infusion development of deep vein thrombosis (DVT), cardiac ischemia, pulmonary embolism (PE), or hemolysis.

Data and Safety Monitoring Board (DSMB). A designated DSMB will formally review subjects' data following the completion of infusions in each cohort for the purpose of assessing safety. DSMB meetings will be scheduled to maximize the amount of subject data reported to the DSMB through the 28-day follow-up visit. The DSMB will have at a minimum all data through the 7-Day Follow Up Visit. Following each meeting, the DSMB will provide the sponsor with a recommendation about proceeding with infusions in the subsequent cohort. Following the meeting to review Cohort 3 data, the DSMB will provide a recommendation about proceeding with the next planned FDP trial. After the receipt and consideration of each DSMB recommendation, the sponsor will make a final determination about proceeding to the next cohort or the next FDP trial.

#### **Estimated Number of Subjects to Screen: 48**

#### Maximum Number of Subjects to Enroll: 24

Cohort 1, Arm 1: (n=4) subjects are to be infused with 1 autologous FDP unit (FDP-CPD) manufactured from WB-derived FFP.

Cohort 1, Arm 2: (n=4) subjects are to be infused with 1 autologous FDP unit (FDP-ACD) manufactured from FFP collected via plasmapheresis.

Cohort 2. Arm 3: (n=4) subjects are to be infused with 2 autologous FDP (FDP-CPD) units manufactured from WB-derived FFP.

Cohort 2, Arm 4: (n=4) subjects are to be infused with 2 autologous FDP units (FDP-ACD) manufactured from FFP collected via plasmapheresis.

Both arms of Cohort 3 are to be infused with 3 units of autologous plasma product at each of 2 infusion visits. Infusion visits are to be scheduled such that there is a period of no less than 2 weeks between infusions.

Cohort 3, Arm 5: (n=4) subjects will receive 3 autologous FDP units (FDP-ACD) manufactured from FFP collected via plasmapheresis at their first infusion visit followed by infusion with 3 autologous FFP units, collected via plasmapheresis, at their second visit.

Cohort 3, Arm 6: (n=4) subjects will be infused with these products in the opposite order as Arm 5 (eg, autologous FFP at first infusion and autologous FDP-ACD at the second).

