# 6.5. Overall Study Design

This single-site, partial double-blind study in healthy volunteers is designed to assess the safety of infusing ascending doses of reconstituted autologous FDP in 3 fixed-dose cohorts. Subjects in Cohort 1 will receive 1 unit of FDP, which is approximately 270 mL. Subjects in Cohort 2 will receive 2 FDP units, which total approximately 540 mL. Cohorts 1 and 2 are the lower-dose cohorts. Subjects will be assigned to these beginning with the lowest dose, Cohort 1. In the absence of TEAEs, SAEs or the implementation of protocol stopping rules (SRs), and with Data and Safety Monitoring Board (DSMB) recommendation and Sponsor approval subjects assigned to Cohort 2 will be infused with an increased dose of 2 units. For both of these cohorts subjects will also be assigned to 1 of 2 single infusion treatment arms:

- 1. Infusion of FDP manufactured with autologous plasma derived from WB (FDP-CPD), at the corresponding dose; or
- 2. Infusion of FDP manufactured with autologous plasma collected by plasmapheresis (FDP-ACD), at the corresponding dose.

In the absence of TEAEs, SAEs, or the implementation of protocol stopping rules (SRs) in Cohort 2 subjects, infusions in Cohort 3 subjects may be implemented. Cohort 3 is designed as a randomized, controlled, crossover infusion of 3 units of FDP (approximately 810 mL) and 3 units of FFP (approximately 810 mL) at separate visits. Subjects are randomized to a specific infusion schedule of either 3 units of FDP or 3 units of FFP at the first infusion visit, followed by infusion with the alternate product at the second infusion visit. Crossover of FDP and FFP enables comparison of infusion safety and select coagulation factor recoveries within the same subjects between FDP and FFP at this higher dose. Unlike Cohorts 1 and 2, the FDP and FFP infusion products in Cohort 3 are sourced solely from autologous plasmapheresis donations (FDP-ACD). A 2-week period between infusion visits is required for all Cohort 3 subjects regardless of infusion schedule.

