## 6.8. Duration of Subject Participation

Subjects in Cohort 1 will complete the study in approximately 3 months. Subjects in Cohort 2, Arm 3 will complete the study in approximately 4 months; subjects in Cohort 2, Arm 4 will require approximately 3 months. Subjects in Cohort 3 will complete the study in approximately 4 months. The first infusion for all cohorts is defined as Study Day 1. Study Day 15 is the second infusion for Cohort 3. The manufacturing time is currently estimated to be 5 weeks and although accounted for in study participation time, no subject activities are planned during this time. Screening and baseline assessment and informed consent visits will require approximately 2 hours. Final eligibility assessments and WB collection or plasmapheresis will require approximately 4 hours. On the day of infusion, the infusion and post-infusion studies will require approximately 8 hours.

For all cohorts, the on-site follow-up assessments will take 1 to 2 hours to complete, and the telephone assessments will take 15 to 20 minutes to complete. Cohorts 1 and 2 will have on-site follow-up assessments on Study Days 2, 8, and 29 and telephone follow-up assessments on Study Days 3, 4, and 15. Cohort 3 will have on-site follow-up assessments on Study Days 2, 8, 16, 22, and 43 and telephone follow-up assessments on Study Days 3, 4, 17, 18, and 29.

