## 14.1.3. Protocol Deviation Procedures

All deviations from the protocol (eg, failure to return for follow-up visits or blood collection within the time indicated in the protocol) are to be documented. The PI or designee will be

responsible for identifying and reporting all deviations, which are defined as isolated occurrences involving a procedure that did not follow the study protocol. Deviations will be reported annually in the continuing review report to the local IRB and the ORP and, if appropriate, in the final study report. Action taken in response to the deviation, and the impact of the deviation will be assessed by the PI and recorded as significant or nonsignificant.

Any protocol deviation that adversely affects the safety or rights of a subject or scientific integrity of the study will be reported immediately to the sponsor's representative, local IRB, and the ORP.

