Just prior to first infusion, subjects will be randomized to a treatment sequence, or schedule, that determines which product, FDP or FFP, is to be administered at the first visit. The blinded subjects will receive the alternate product during the second infusion. Product treatment crossover at this higher fixed dose allows for comparison of safety between the two products within the same subject and it allows for the comparison of recovery of select coagulation factors and proteins post-infusion with each product. A two-week interval between each Cohort 3 subject's infusion visits is required regardless of the product treatment sequence.

If any of the stopping rules (SRs) occur throughout the trial, the study will be paused to assess continuation of the study:

1. A serious adverse event (SAE) that is determined to be possibly, probably, or definitely related to the study product;
2. An adverse event (AE) related to the study product that the Principal Investigator (PI), Research Monitor (RM), and/or the sponsor's Pharmacovigilance Physician (PVG MD) agree jeopardizes the subject's health or safety;
3. An AE related to the study product that requires medical or surgical intervention to prevent occurrence of an SAE;
4. A post-infusion, abnormal coagulation function assay which is also a greater than 20% change from baseline for prothrombin time and international normalized ratio (PT/INR) and/or activated

partial thromboplastin time (aPTT) values (e.g., a subject who has a baseline INR of 1.0 with a post-infusion INR of 1.3 will activate a SR, because this is an abnormal coagulation function assay result that is also a greater than 20% change from the pre-infusion assay result); and/or

5. Post-infusion development of hemolysis or deep vein thrombosis (DVT), cardiac ischemia, or pulmonary embolism. DVT will be determined following the Institute for Clinical Systems Improvement Health Care Guideline: Venous Thromboembolism Diagnosis and Treatment (includes assessment of D-Dimer results and Wells criteria ≥ 2). (Dupras et al-2013).

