2.2.3 Infusion Visit(s)

The infusion visit for the first subject in each cohort is to occur approximately five weeks following his or her last collection visit. Unlike Cohorts 1 and 2 subjects, Cohort 3 subjects require two infusion visits. These are to occur with no less than a two-week interval in between infusions. Subjects will undergo autologous infusion at each of these visits according to the corresponding treatment specifications of the arm to which they belong.

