IND # 17154; S-14-12
CONFIDENTIAL
[1] C=Compatible N=Not Compatible.

The Surgeon General
Department of the Army

Program Path:
Data source: ADLB

Data extract date:

10

Listing 8. FDP-CPD/FDP-ACD/FFP – Subject Exposure to Study Drug

Arm: XXXXXX

Subject ID	Sex/Age	Date of Enrollment	Randomization Date	Infusion Start Date for First Infusion	Infusion Start Date for Second Infusion	Weight (kg)	Total Amount Administered at First Infusion (mL)	Total Amount Administered at Second Infusion (mL)	Dose Adjusted from Planned	Reason Dose Adjusted from Planned
XXXXXX	X/XX	DDMMYY	DDMMYY	DDMMYY	DDMMYY	XXX.X	XXX.X	XXX.X	X	XXXXXXXXXX
XXXXXX	X/XX	DDMMYY	DDMMYY	DDMMYY	DDMMYY	XXX.X	XXX.X	XXX.X	X	XXXXXXXXXX
XXXXXX	X/XX	DDMMYY	DDMMYY	DDMMYY	DDMMYY	XXX.X	XXX.X	XXX.X	X	XXXXXXXXXX
XXXXXX	X/XX	DDMMYY	DDMMYY	DDMMYY	DDMMYY	XXX.X	XXX.X	XXX.X	X	XXXXXXXXXX
XXXXXX	X/XX	DDMMYY	DDMMYY	DDMMYY	DDMMYY	XXX.X	XXX.X	XXX.X	X	XXXXXXXXXX

Listing 9. Medical History at Screening

Arm: XXXXXX

Subject ID	Sex/Age	Date of Informed Consent	Screen Date	Medical History Term
XXXXXX	X/XX	DDMMYY	DDMMYY	XXXXXXXXXXXXXXXXXXXXXXXXXXXX
XXXXXX	X/XX	DDMMYY	DDMMYY	XXXXXXXXXXXXXXXXXXXXXXXXXXXX
XXXXXX	X/XX	DDMMYY	DDMMYY	XXXXXXXXXXXXXXXXXXXXXXXXXXXX
XXXXXX	X/XX	DDMMYY	DDMMYY	XXXXXXXXXXXXXXXXXXXXXXXXXXXX
XXXXXX	X/XX	DDMMYY	DDMMYY	XXXXXXXXXXXXXXXXXXXXXXXXXXXX

Listing 10. Vital Signs (Infusion – Post Start)

Arm: XXXXXXX

Subject ID	Sex/Age	Infusion Number [1]	Visit	Collection Date/Time	Vital Sign Test	Result	Unit
XXXXXX	X/XX	X	X	DDMMYY:TT	XXXXX	XXXXX	XXXXX
		X	X	DDMMYY:TT	XXXXX	XXXXX	XXXXX
		X	X	DDMMYY:TT	XXXXX	XXXXX	XXXXX
		X	X	DDMMYY:TT	XXXXX	XXXXX	XXXXX
XXXXXX	X/XX	X	X	DDMMYY:TT	XXXXX	XXXXX	XXXXX
		X	X	DDMMYY:TT	XXXXX	XXXXX	XXXXX
		X	X	DDMMYY:TT	XXXXX	XXXXX	XXXXX
		X	X	DDMMYY:TT	XXXXX	XXXXX	XXXXX

[1] Infusion Number: 1=Infusion #1; 2=Infusion #2.

Program Path:
Data source: ADVS

Data extract date:

Listing 11. Vital Signs (Infusion – Post End)

Arm: XXXXXX

Subject ID	Sex/Age	Infusion Number [1]	Visit	Collection Date/Time	Vital Sign Test	Result	Unit
XXXXXX	X/XX	X	X	DDMMYY:TT	XXXXX	XXXXX	XXXXX
		X	X	DDMMYY:TT	XXXXX	XXXXX	XXXXX
		X	X	DDMMYY:TT	XXXXX	XXXXX	XXXXX
		X	X	DDMMYY:TT	XXXXX	XXXXX	XXXXX
XXXXXX	X/XX	X	X	DDMMYY:TT	XXXXX	XXXXX	XXXXX
		X	X	DDMMYY:TT	XXXXX	XXXXX	XXXXX
		X	X	DDMMYY:TT	XXXXX	XXXXX	XXXXX
		X	X	DDMMYY:TT	XXXXX	XXXXX	XXXXX

[1] Infusion Number: 1=Infusion #1; 2=Infusion #2.

Program Path:
Data source: ADVS

Data extract date:

Listing 12. Vital Signs (Outside of Infusion)

Arm: XXXXXX

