						Collection Date/Time	Result in Original Units	Collection Date/Time	Result in Original Units
XXXXXX	X/XX	XXXXXXXX	XXXX	XXXXX	XXXXX	DDMMYYYY:TT	XXXXX	DDMMYYYY:TT	XXXXX
				XXXXX	XXXXX	DDMMYYYY:TT	XXXXX	DDMMYYYY:TT	XXXXX
				XXXXX	XXXXX	DDMMYYYY:TT	XXXXX	DDMMYYYY:TT	XXXXX
				XXXXX	XXXXX	DDMMYYYY:TT	XXXXX	DDMMYYYY:TT	XXXXX
				XXXXX	XXXXX	DDMMYYYY:TT	XXXXX	DDMMYYYY:TT	XXXXX

Listing 35. Additional Screening Results for Subjects Rescreened

Arm: XXXXXXX

Subject ID	Sex/Age	Category for Lab Test	Visit Name	Lab Test	Unit	Original Measurement		Repeated Measurement	
						Collection Date/Time	Result in Original Units	Collection Date/Time	Result in Original Units
XXXXXX	X/XX	XXXXXXXX	XXXX	XXXXX	XXXXX	DDMMYYYY:TT	XXXXX	DDMMYYYY:TT	XXXXX
				XXXXX	XXXXX	DDMMYYYY:TT	XXXXX	DDMMYYYY:TT	XXXXX
				XXXXX	XXXXX	DDMMYYYY:TT	XXXXX	DDMMYYYY:TT	XXXXX
				XXXXX	XXXXX	DDMMYYYY:TT	XXXXX	DDMMYYYY:TT	XXXXX
				XXXXX	XXXXX	DDMMYYYY:TT	XXXXX	DDMMYYYY:TT	XXXXX

Listing 36. Prior Concomitant Medications

Arm: XXXXXXX

Subject ID	Sex/Age	Date of Enrollment	Randomization Date	Start Date	End Date [1]	Medication or Therapy	Dose (units)	Frequency	Route of Admin [2]	Indication
XXXXXX	X/XX	DDMMYYYYYY	DDMMYYYYYY	DDMMYYYYYY	DDMMYYYYYY	XXXXXXXXXXXX	XXX (XX)	XXXXX	XXXX	XXXXXXX
		DDMMYYYYYY	DDMMYYYYYY	DDMMYYYYYY	DDMMYYYYYY	XXXXXXXXXXXX	XXX (XX)	XXXXX	XXXX	XXXXXXX
		DDMMYYYYYY	DDMMYYYYYY	DDMMYYYYYY	DDMMYYYYYY	XXXXXXXXXXXX	XXX (XX)	XXXXX	XXXX	XXXXXXX
		DDMMYYYYYY	DDMMYYYYYY	DDMMYYYYYY	DDMMYYYYYY	XXXXXXXXXXXX	XXX (XX)	XXXXX	XXXX	XXXXXXX
		DDMMYYYYYY	DDMMYYYYYY	DDMMYYYYYY	DDMMYYYYYY	XXXXXXXXXXXX	XXX (XX)	XXXXX	XXXX	XXXXXXX
XXXXXX	X/XX	DDMMYYYYYY	DDMMYYYYYY	DDMMYYYYYY	DDMMYYYYYY	XXXXXXXXXXXX	XXX (XX)	XXXXX	XXXX	XXXXXXX
		DDMMYYYYYY	DDMMYYYYYY	DDMMYYYYYY	DDMMYYYYYY	XXXXXXXXXXXX	XXX (XX)	XXXXX	XXXX	XXXXXXX
		DDMMYYYYYY	DDMMYYYYYY	DDMMYYYYYY	DDMMYYYYYY	XXXXXXXXXXXX	XXX (XX)	XXXXX	XXXX	XXXXXXX
		DDMMYYYYYY	DDMMYYYYYY	DDMMYYYYYY	DDMMYYYYYY	XXXXXXXXXXXX	XXX (XX)	XXXXX	XXXX	XXXXXXX
		DDMMYYYYYY	DDMMYYYYYY	DDMMYYYYYY	DDMMYYYYYY	XXXXXXXXXXXX	XXX (XX)	XXXXX	XXXX	XXXXXXX

[1] Drugs continuing at the end of the study are labelled as ongoing.

[2] IL = Intralesional; IP = Intraperitoneal; R = Rectal; TOP = Topical.

IM = Intramuscular; N = Nasal; INH = Respiratory (Inhalation); TD = Transdermal.

IO = Intraocular; PO = Oral; SC = Subcutaneous; VAGL = Vaginal.

Program Path:

Data source: ADSL, CM

Data extract date:

Listing 37. Protocol Deviations

Arm: XXXXXXX

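### The Table 8 window for Cohort 3 infusion 2 (± 3 days around Day 15) permits gaps of 11 to 13 days, below the stated two-week minimum

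*Protocol*

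**What the plan says.** The synopsis, in its enrolment paragraph for Cohort 3, sets a minimum: "Infusion visits are to be scheduled such that there is a period of no less than 2 weeks between infusions". SAP 2.2.3 repeats it for the two infusion visits: "These are to occur with no less than a two-week interval in between infusions". Protocol 6.5 describes the interval as mandatory: "A 2-week period between infusion visits is required for all Cohort 3 subjects regardless of infusion schedule". SAP 1.1 likewise says that a two-week gap between each subject's "infusion visits is required regardless of the product treatment sequence".

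Protocol 6.8 defines the first infusion as Study Day 1 and adds: "Study Day 15 is the second infusion for Cohort 3". Protocol 8.2.2 gives the same two days.

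Table 8, the Cohort 3 events schedule, lists Visit 6 (Infusion #2) on Day 15 with a window of ± 3 days. The entry is the same in all three parts of the table, and no footnote restricts its early side.

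Protocol 11.1.1 and SAP 4.5.3.1 attribute a Cohort 3 adverse event within 14 days of an infusion, as a general rule, to the product infused most recently. Both allow exceptions.

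**The concern.** The planned gap sits exactly on the floor, so a symmetric window must cross it. The schedule and the text then give the site two rules for the crossover interval, and the table, which is what staff are likely to schedule from, carries the looser one.

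Two things are at stake.

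- **Detection.** SAP 4.4.1 refers to the protocol's events schedule for visit windows and treats results outside them as deviations. SAP Listing 4 records whether each visit fell in its window. A Day 12 infusion passes both checks although it breaks the stated minimum.
- **Attribution.** The 14-day default period matches the 14-day floor. With a gap of at least 14 days, the first product keeps its whole period. With a shorter gap, events on the missing days go by default to the second product. That bears on the comparison of freeze dried plasma with fresh frozen plasma under the first secondary objective.

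There is a smaller related point. Protocol 8.3.2 omits the 14-day call after infusion 1 because it would coincide with infusion 2. If infusion 2 moves to Day 12, that reason no longer applies, and the last adverse event review before the second product takes place 11 days after the first.

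**Working it through.** **Inputs**

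- Infusion 1: Day 1 (Protocol 6.8).
- Infusion 2: Day 15 (Protocol 6.8 and 8.2.2; Table 8, Visit 6).
- Window for infusion 2: ± 3 days (Table 8, all three parts).
- Minimum gap: 14 days (synopsis; SAP 2.2.3).
- Default attribution period: 14 days (Protocol 11.1.1; SAP 4.5.3.1).
- Seven-day visit after infusion 1: Day 8 ± 1 day (Table 8, Visit 5).

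**The plan's own figure.** Gap = day of infusion 2 − day of infusion 1 = 15 − 1 = 14 days. This reproduces the stated two weeks, with no slack.

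**Every day in the window.** The window runs from 15 − 3 = Day 12 to 15 + 3 = Day 18, which is 7 days. Attribution days lost = 14 − gap, where positive.

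| Day of infusion 2 | Gap (days) | Meets 14-day minimum | Attribution days lost by first product |
|---|---|---|---|
| 12 | 11 | No | 3 (3/14 = 21.4%) |
| 13 | 12 | No | 2 (2/14 = 14.3%) |
| 14 | 13 | No | 1 (1/14 = 7.1%) |
| 15 | 14 | Yes | 0 |
| 16 | 15 | Yes | 0 |
| 17 | 16 | Yes | 0 |
| 18 | 17 | Yes | 0 |

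Three of the 7 in-window days break the minimum. Only the early side conflicts.

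**Is any visit after infusion 1 lost?** The latest in-window seven-day visit is 8 + 1 = Day 9. The earliest in-window infusion 2 is Day 12, which is 12 − 9 = 3 days later. No scheduled visit is displaced.

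**With a one-sided window (0/+3).** Days 15 to 18 give gaps of 14 to 17 days. That leaves 4 permitted days, none below the minimum.

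**The case against.** The strongest reply is that the two rules are compatible. A window is a tolerance and a minimum is a constraint, so a site bound by both uses Days 15 to 18. An earlier infusion would remain a protocol deviation: Protocol 14.1.3 makes the investigator or designee "responsible for identifying and reporting all deviations, which are defined as isolated occurrences involving a procedure that did not follow the study protocol". The SAP has somewhere to record it ("Listing 37. Protocol Deviations"), and Listing 8 shows the first infusion date beside the "Infusion Start Date for Second Infusion". All of this is correct, and it means a breach can be found. It does not make the table right, because neither document says that the text overrides the window.

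A second reply is that an explicit floor appears only in the synopsis and the SAP. The body of the protocol speaks of a two-week interval (5.7), a required two-week period (6.5) and Days 1 and 15 (8.2.2), which could be read as nominal. Loosening the synopsis and SAP 2.2.3 would then also remove the conflict. That is a possible repair, but an explicit minimum in both documents, matched by the 14-day attribution period, points to narrowing the table.

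A third reply is that little changes in the results. The analysis is descriptive (SAP 4.5.1), baselines are taken afresh before each infusion (SAP 4.4.2), and out-of-window results are still analysed (SAP 4.4.1). The final adverse event shells label Cohort 3 by sequence, so moving an event between products does not move a subject between columns. This does limit the effect on the tables. It does not remove it, since Protocol 11.1.1 and SAP 4.5.3.1 still call for attribution and presentation by product.

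Finally, Protocol 6.3 leaves procedural detail to the Manual of Procedures, which was not available for review and may already restrict the early side.

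**Conclusion.** The inconsistency is real and should be corrected. As written, Table 8 accepts three days (12, 13 and 14) on which the second infusion would break the two-week minimum, by 3, 2 and 1 days respectively.

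The consequence is limited. For a subject infused early, the first product's default attribution period falls from 14 days to between 11 and 13. The percentages are shares of calendar days, not of events, and they apply only to subjects infused early. No event is counted twice, and exceptions to the attribution rule are allowed.

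The conclusion assumes that gaps are counted in whole study days and that no restriction exists outside the two documents. It does not claim that early infusions will occur or that an 11-day gap is pharmacologically too short.

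**What to change.** In Table 8, change the Visit 6 (Infusion #2) window from ± 3 days to 0/+3 days, Day 15 to Day 18, in each of the three parts. If the Manual of Procedures repeats the window, align it too.

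The edit is three table cells. Under Protocol 14.1.2 it needs review and approval before use, including by the sponsor's representative and the local IRB. A site scheduling from the table goes from 7 permitted days to 4; a site already observing the minimum loses nothing. Endpoints, sample size and analyses are unchanged.
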